14.2 Demographic and Baseline Characteristics

The following demographic variables at screening will be summarized by dose level: gender, age, height and weight.

14.3 Analysis of Primary Endpoint

Student t test will be used for significance analysis.

14.4 Analysis of Secondary Endpoints

Student t test will be used for significance analysis.

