4 STUDY DESIGN

4.1 Study Overview

This is a single center, open-label, controlled, randomized, phase II clinical trial. 200 of subjects are planned. Each subject will be administered a single dose (500 mg) of study drug twice daily for 10 days. Subjects will be assigned to the treatments in random order. Evaluations will be taken daily for evaluationg symptoms imrovpment.

Screening data will be reviewed to determine subject eligibility. Subjects who meet all inclusion criteria and none of the exclusion criteria will be entered into the study.

The following treatment regimens will be used:

- Experimental treatment NS at the following dose 500 mg twice daily
- Comparator Standard care for COVID-19

Total duration of subject participation will be 14 days. Total duration of the study is expected to be 12 months.

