5.2 Secondary Efficacy Endpoints

- Improvement of Clinical Parameters:
- o Time to full clinical recovery
- o Time to progression to pneumonia or hypoxia
- o Duration of illness
- o Discharge to home
- o Normalization of chest radiograph.

o Rate of complications: ICU admission, noninvasive ventilator, superadded infection o Death.

- Normalization of Routine Laboratory Tests:
- o Complete Blood Count (CBC)

o Erythrocyte sedimentation rate (ESR)

o C-reactive protein

o D-dimer

o Liver function test

o Renal function test

o Lactate Dehydrogenase (LDH),

o Immunoglobulins (IgA, IgE, IgG, IgM),

o Compliments (c3, c4),

o Chest X-ray, CT scan

o COVID-19 PCR

o Immune phenotype (CD3 T Cell, CD4 T Cell, CD8 T Cell, CD19 B Cell, CD20 B Cell, NK Cell)

- Additional:

o Inflammatory cytokines (IL-1β, IL-1Ra, IL-2, IL-6, IL-10, INF-alpha, INF-gamma, Eotaxin, RANTES & TNF-α).

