8.3 Formulation of Test and Control Products

SFDA-licensed Marnys CUMINMAR Nigella sativa oil 500mg softgel oral capsules.

No control product will be used.

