12 DISCONTINUATION AND REPLACEMENT OF SUBJECTS

12.1 Early Discontinuation of Study Drug

A subject may be discontinued from study treatment at any time if the subject, the investigator, or the Sponsor feels that it is not in the subject's best interest to continue. The following is a list of possible reasons for study treatment discontinuation:

- Subject withdrawal of consent (or assent)
- Subject is not compliant with study procedures
- Adverse event that in the opinion of the investigator would be in the best interest of the subject to discontinue study treatment
- Protocol violation requiring discontinuation of study treatment
- Lost to follow-up
- Sponsor request for early termination of study
- Positive pregnancy test (females)

If a subject is withdrawn from treatment due to an adverse event, the subject will be followed and treated by the medical research team until the abnormal parameter or symptom has resolved or stabilized.

All subjects who discontinue study treatment should come in for an early discontinuation visit as soon as possible and then should be encouraged to complete all remaining scheduled visits and procedures.

All subjects are free to withdraw from participation at any time, for any reason, specified or unspecified, and without prejudice.

Reasonable attempts will be made by the investigator to provide a reason for subject withdrawals. The reason for the subject's withdrawal from the study will be specified in the subject's source documents Refer to Section 10 for early termination procedures.

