12.3 Withdrawal of Subjects from the Study

A subject may be withdrawn from the study at any time if the subject, the investigator, or the Sponsor feels that it is not in the subject's best interest to continue.

All subjects are free to withdraw from participation at any time, for any reason, specified or unspecified, and without prejudice.

Reasonable attempts will be made by the investigator to provide a reason for subject withdrawals. The reason for the subject's withdrawal from the study will be specified in the subject's source documents. As noted above, subjects who discontinue study treatment early (i.e., they withdraw prior to Visit 1) should have an early discontinuation visit. Refer to Section 10 for early termination procedures. Subjects who withdraw after Visit 1 should

be encouraged to come in for a final visit (and the procedures to be followed would include those for their next scheduled visit).

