12.4 Replacement of Subjects

Subjects who withdraw from the study treatment will be replaced.

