14 STATISTICAL METHODS AND CONSIDERATIONS

14.1 Data Sets Analyzed

All dosed subjects will be included in data analysis

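### Section 14.4 assigns the Student t test to time-to-event secondary endpoints and gives no rule for patients without the event at the end of follow-up or lost earlier

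*Combined protocol and SAP*

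**What the plan says.** Section 14.4 is a single sentence covering every secondary endpoint: "Student t test will be used for significance analysis". Section 14.3 and the synopsis name the same test for the primary endpoint. No other test is named.

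Section 5.2 lists three endpoints that are times: time to recovery, "Time to progression to pneumonia or hypoxia", and duration of illness. Section 4.1 fixes the observation period: "Total duration of subject participation will be 14 days". Incomplete observation is foreseen. Section 12.1 lists "Lost to follow-up" among the reasons for stopping study treatment, and section 12.3 says "All subjects are free to withdraw from participation at any time, for any reason, specified or unspecified, and without prejudice".

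Two statements bear on these patients. Section 14.1 says "All dosed subjects will be included in data analysis", and section 12.4 says "Subjects who withdraw from the study treatment will be replaced". Neither gives a time to a patient whose event was not observed. The word for treated patients in 14.1 is also unclear for the comparator arm, since section 8.3 states "No control product will be used".

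No time origin is given for the three time endpoints. Elsewhere the plan uses more than one clock:
- Section 5.1 counts 14 days from symptom onset.
- Section 3.1 and the synopsis statistics refer to the 10-day treatment period.
- The synopsis lists up to 7 days of screening, 10 of treatment and 14 of follow-up, beside participation of up to 14 days.

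**The concern.** A t test compares means of fully observed values. For a patient who has not recovered or progressed when observation stops, it is known only that the time exceeds the last day seen. The analyst must therefore drop that patient or choose a value. The plan makes neither choice, so it would be made after an open-label trial has produced data.

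The choice matters most for progression, where most patients may have no event. Entering the last observed day treats a patient lost on Day 4 as if progression occurred on Day 4. If one arm loses more patients, its mean time falls for that reason alone.

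Time to recovery also carries more weight than a routine secondary endpoint, because the primary objective in section 3.1 is worded as a recovery period.

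**Working it through.** **No figure to reproduce.** The plan gives no event rate, hazard ratio, dropout rate or power for any time endpoint. The 200 patients in section 14.5 are justified on a difference in proportions. Only 100 per arm, 14 days and a two-sided 5% level are taken from the documents. All rates below are assumptions.

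**1. Early loss, last observed day entered, no treatment effect on progression.** Assume that 10% progress in each arm, at times spread evenly over 14 days. A proportion d drops out independently, also evenly. Let S = 14 minus the recorded day.

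- Share with exactly one of the two times inside 14 days: a = 0.10(1 − d) + 0.90d. Here S has mean 7 and mean square 196/3 = 65.33.
- Share with both: b = 0.10d. The earlier time counts, so S has mean 28/3 = 9.33 and mean square 98.
- Mean of S = 7a + 9.33b. Variance = 65.33a + 98b − mean².

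For 5% vs 15% dropout:

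- d = 0.05: a = 0.14, b = 0.005; mean = 0.98 + 0.047 = 1.027; variance = 9.147 + 0.490 − 1.054 = 8.583.
- d = 0.15: a = 0.22, b = 0.015; mean = 1.54 + 0.14 = 1.680; variance = 14.373 + 1.470 − 2.822 = 13.021.
- Difference = 0.653 day; SE = √[(8.583 + 13.021)/100] = 0.465; ratio = 1.41.
- Rejection probability ≈ P(Z > 1.96 − 1.41) = 29%, where 5% is nominal.

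The same steps give the other rows. The simulated columns come from 10,000 or more trials per scenario for the t test; the log-rank range also covers repeat runs.

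| Dropout by arm | Difference (days) | SE | Ratio | Formula | t test, simulated | Log-rank, simulated |
|---|---|---|---|---|---|---|
| equal (5% vs 5% in formula) | 0 | 0.414 | 0 | 5% | 5% | 4–6% |
| 2% vs 5% | 0.196 | 0.396 | 0.50 | 8% | 7% | 4–6% |
| 5% vs 10% | 0.327 | 0.442 | 0.74 | 11% | 11% | 4–6% |
| 5% vs 15% | 0.653 | 0.465 | 1.41 | 29% | 28% | 4–6% |

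The inflation is the same whichever arm has the excess. Log-rank is protected only when dropout is unrelated to outcome. If half of the progressors in the Nigella sativa arm were lost just before the event, its own error would be 24%.

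**2. Complete follow-up, patients without the event entered at Day 14.** The t test keeps its 5% error. Power for time to recovery, with times rounded up to whole days:

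| Assumed recovery times | t test | Log-rank |
|---|---|---|
| Exponential, control median 7, HR 1.5 | 68.5% | 73.5% |
| Exponential, control median 7, HR 1.6 | 81.0% | 85.3% |
| Exponential, control median 10, HR 1.5 | 60.0% | 66.9% |
| Exponential, control median 10, HR 1.6 | 73.5% | 80.4% |
| Log-normal, medians 7 vs 5.5, sigma 0.6 | 79% | 75% |
| Log-normal, medians 10 vs 8, sigma 0.6 | 70% | 66% |
| Log-normal, medians 7 vs 5.8, sigma 0.5 | 72% | 68% |
| Log-normal, medians 10 vs 8.5, sigma 0.5 | 60% | 57% |

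Under proportional hazards log-rank gains about 4 to 7 points. Under these log-normal models the t test gains 3 to 4.

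**3. Primary endpoint.** On simulated 0/1 data with recovery between 30% and 90%, the t test and chi-square reached the same decision in 99.8–100% of trials.

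**4. Clocks.** Symptom onset precedes randomisation by an interval that varies between patients, so 14 days from onset and 14 days on study need not end together. Read consecutively, the synopsis's treatment and follow-up make 10 + 14 = 24 days, which does not fit 14 days of participation. The day of administrative censoring is therefore also unsettled.

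**The case against.** The strongest reply is that a t test on times capped at Day 14 is legitimate: with complete follow-up it compares restricted mean times. That stands. A reader might infer that the t test must cost power here; the second table shows that the sign depends on the time distribution, about which the documents say nothing.

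Next, the inflated error rates need two inputs that the plan does not contain: entry of the last observed day, and unequal dropout. That also stands. The figures show what the gap permits; they do not forecast this trial's error rate.

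Retention may be good. There is one site, follow-up is short and evaluation is daily. Section 12.1 encourages patients who stop treatment to complete the remaining visits, and section 12.3 asks those who withdraw for a final visit. Loss to follow-up is listed there as a reason for stopping treatment. This makes a large imbalance less likely, but it does not say how a lost patient is analysed.

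Finally, these are unpowered secondary endpoints in a trial that the synopsis calls exploratory. That limits the severity. It does not make the named test suitable for censored times.

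**Conclusion.** The concern holds: the only test named for the time endpoints cannot use right-censored times without an assigned value, and the plan assigns none. Confidence in that reading of the text is high. The sizes are illustrations on assumed rates: no inflation with equal dropout, 7–11% error at the smaller imbalances and 28% at 5% vs 15%, all conditional on last-day entry. It should be fixed, but it does not undermine the primary result.

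Three stronger readings are not supported:
- A reader might infer that patients without the event would be left out. Section 14.1 points the other way.
- A reader might infer that the onset-based window is the plan's only clock. The synopsis and section 3.1 also use the treatment period, so the defect is several unreconciled clocks and none assigned to these endpoints.
- A reader might infer that the t test would change the primary decision. It would almost never do so; what is lost there is a suitable estimate.

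**What to change.** In section 14.4, for the time endpoints:
- Replace the t test with Kaplan-Meier curves, a log-rank test and a Cox hazard ratio in all randomised patients.
- Use randomisation as the time origin, and censor at last contact or the end of follow-up.
- For recovery, keep patients who die as not recovered to the end of follow-up.
- For progression, state in advance whether death without prior progression is an event or a competing event.
- Add a sensitivity analysis for progression that counts dropouts as progressed, since log-rank is not protected against outcome-related loss.

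Reconcile the onset-based window in section 5.1 with the treatment-based wording in section 3.1 and the synopsis, and with the participation and follow-up durations in section 4.1 and the synopsis.

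For yes/no outcomes, including the primary in section 14.3 and the synopsis, report a chi-square or Fisher's exact test with the risk difference and its 95% CI. For the primary this improves the estimate and leaves the decision essentially unchanged.

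The cost is small. Sample size and treatment do not change. The origin and death rules complete the endpoint definitions, so they need agreement as well as wording. Section 10.2 lists symptom recording over 14 days but no pneumonia or hypoxia check, and the Appendix 1 schedule is not in the documents provided. Confirm that the case report form captures the dates of progression and last contact.

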14.5 Sample Size and Randomization

To achieve a power of 80% and a two-tailed p-value of <0.05 of an assumed 40% difference between the proportion of patients with clinical cure among the NS group in comparison with the control group, a total of at least 200 patients assigned randomly into the two arms (ie 100 patients per arm) will be needed to be included in the study as

calculated using G*Power version 3.1.9.2 (Heinrich-Heine-University Düsseldorf, Düsseldorf, Germany).

15 DATA COLLECTION, RETENTION AND MONITORING

15.1 Data Collection Instruments

The Investigator will prepare and maintain adequate and accurate source documents designed to record all observations and other pertinent data for each subject treated with the study drug.

Study personnel at each site will enter data from source documents corresponding to a subject's visit into the protocol-specific paper CRF when the information corresponding to that visit is available. Subjects will not be identified by name in the study database or on any study documents to be collected by the Sponsor (or designee), but will be identified by a subject number.

The Investigator is responsible for all information collected on subjects enrolled in this study. All data collected during the course of this study must be reviewed and verified for completeness and accuracy by the Investigator. A copy of the CRF will remain at the Investigator's site at the completion of the study.

15.2 Data Management Procedures

The data will be entered into a validated database. The investigator will be responsible for data processing, in accordance with procedural documentation.

All procedures for the handling and analysis of data will be conducted using good computing practices meeting SFDA guidelines for the handling and analysis of data for clinical trials.

15.3 Data Quality Control and Reporting

NA

15.4 Archival of Data

The database is safeguarded against unauthorized access by established security procedures; appropriate backup copies of the database and related software files will be maintained. Databases are backed up by the database administrator in conjunction with any updates or changes to the database.

At critical junctures of the protocol (e.g., production of interim reports and final reports), data for analysis is locked and cleaned per established procedures.

15.5 Availability and Retention of Investigational Records

The Investigator must make study data accessible to the monitor, other authorized representatives of the Sponsor (or designee), IRB/IEC, and Regulatory Agency (e.g., SFDA) inspectors upon request. A file for each subject must be maintained that includes the CRF. The Investigator must ensure the reliability and availability of source documents from which the information on the CRF was derived.

All study documents (copies of CRFs) must be kept secured for a period of two years following marketing of the investigational product or for two years after centers have been notified that the IND has been discontinued. There may be other circumstances for which the Sponsor is required to maintain study records and, therefore, the Sponsor should be contacted prior to removing study records for any reason.

15.6 Monitoring

NA

15.7 Subject Confidentiality

In order to maintain subject confidentiality, only a site number, subject number and subject initials will identify all study subjects on CRFs and other documentation submitted to the Sponsor. Additional subject confidentiality issues (if applicable) are covered in the Clinical Study Agreement.

16 ADMINISTRATIVE, ETHICAL, REGULATORY CONSIDERATIONS

The study will be conducted according to the Declaration of Helsinki, Protection of Human Volunteers (21 CFR 50), Institutional Review Boards (21 CFR 56), and Obligations of Clinical Investigators (21 CFR 312).

To maintain confidentiality, all laboratory specimens, evaluation forms, reports and other records will be identified by a coded number and initials only. All study records will be kept in a locked file cabinet and code sheets linking a patient's name to a patient identification number will be stored separately in another locked file cabinet. Clinical information will not be released without written permission of the subject, except as necessary for monitoring by the SFDA. The Investigator must also comply with all applicable privacy regulations (e.g., Health Insurance Portability and Accountability Act of 1996, EU Data Protection Directive 95/46/EC).

16.1 Protocol Amendments

Any amendment to the protocol will be written by the Sponsor. Protocol amendments cannot be implemented without prior written IRB/IEC approval except as necessary to eliminate immediate safety hazards to patients. A protocol amendment intended to eliminate an apparent immediate hazard to patients may be implemented immediately, provided the IRBs are notified within five working days.

16.2 Institutional Review Boards and Independent Ethics Committees

The protocol and consent form will be reviewed and approved by the IRB/IEC of King Abdulaziz University Hospital. Serious adverse experiences regardless of causality will be reported to the IRB/IEC in accordance with the standard operating procedures and policies of the IRB/IEC, and the Investigator will keep the IRB/IEC informed as to the progress of the study. The Investigator will obtain assurance of IRB/IEC compliance with regulations.

Any documents that the IRB/IEC may need to fulfill its responsibilities (such as protocol, protocol amendments, Investigator's Brochure, consent forms, information concerning patient recruitment, payment or compensation procedures, or other pertinent information)

will be submitted to the IRB/IEC. The IRB/IECs written unconditional approval of the study protocol and the informed consent form will be in the possession of the Investigator before the study is initiated. This approval must refer to the study by exact protocol title and number and should identify the documents reviewed and the date of review.

Protocol and/or informed consent modifications or changes may not be initiated without prior written IRB/IEC approval except when necessary to eliminate immediate hazards to the patients or when the change(s) involves only logistical or administrative aspects of the study. Such modifications will be submitted to the IRB/IEC and written verification that the modification was submitted and subsequently approved should be obtained.

The IRB/IEC must be informed of revisions to other documents originally submitted for review; serious and/or unexpected adverse experiences occurring during the study in accordance with the standard operating procedures and policies of the IRB; new information that may affect adversely the safety of the patients of the conduct of the study; an annual update and/or request for re-approval; and when the study has been completed.

16.3 Informed Consent Form

Informed consent will be obtained in accordance with the Declaration of Helsinki, ICH GCP, US Code of Federal Regulations for Protection of Human Subjects (21 CFR 50.25[a,b], CFR 50.27, and CFR Part 56, Subpart A), the Health Insurance Portability and Accountability Act (HIPAA, if applicable), and local regulations.

The Investigator will prepare the informed consent form and submit to the IRB/IEC. The consent form generated by the Investigator must be acceptable to the Sponsor and be approved by the IRB/IEC. The written consent document will embody the elements of informed consent as described in the International Conference on Harmonisation and will also comply with local regulations. The Investigator will send an IRB/IEC-approved copy of the Informed Consent Form to the Sponsor (or designee) for the study file.

A properly executed, verbal informed consent will be obtained from each subject prior to entering the subject into the trial. Information should be given in both oral and written form and subjects (or their legal representatives) must be given ample opportunity to inquire about details of the study. If appropriate and required by the local IRB/IEC, assent from the subject will also be obtained.

16.4 Publications

The preparation and submittal for publication of manuscripts containing the study results shall be in accordance with a process determined by mutual written agreement among the study Sponsor and participating institutions. The publication or presentation of any study results shall comply with all applicable privacy laws, including, but not limited to, the Health Insurance Portability and Accountability Act of 1996.

16.5 Investigator Responsibilities

By signing the Agreement of Investigator form, the Investigator agrees to:

- 1. Conduct the study in accordance with the protocol and only make changes after notifying the Sponsor (or designee), except when to protect the safety, rights or welfare of subjects.
- 2. Personally, conduct or supervise the study (or investigation).
- 3. Ensure that the requirements relating to obtaining informed consent and IRB review and approval meet federal guidelines, as stated in § 21 CFR, parts 50 and 56.
- 4. Report to the Sponsor or designee any AEs that occur in the course of the study, in accordance with §21 CFR 312.64.
- 5. Ensure that all associates, colleagues and employees assisting in the conduct of the study are informed about their obligations in meeting the above commitments.
- 6. Maintain adequate and accurate records in accordance with §21 CFR 312.62 and to make those records available for inspection with the Sponsor (or designee).
- 7. Ensure that an IRB that complies with the requirements of §21 CFR part 56 will be responsible for initial and continuing review and approval of the clinical study.
- 8. Promptly report to the IRB and the Sponsor (or designee) all changes in the research activity and all unanticipated problems involving risks to subjects or others (to include amendments and IND safety reports).
- 9. Seek IRB approval before any changes are made in the research study, except when necessary to eliminate hazards to the patients/subjects.
- 10. Comply with all other requirements regarding the obligations of clinical investigators and all other pertinent requirements listed in § 21 CFR part 312
